## 1.4 Study Design

This study is a randomized, double-blind, placebo-controlled, multicenter parallel group study assessing the effects of rosuvastatin 20 mg treatment for 104 weeks on the change in IMT of the common carotid artery (CCA), carotid bulb, and internal carotid artery (ICA) in adult Chinese subjects with subclinical atherosclerosis. The study will be conducted across approximately 30 sites in China. The study design is illustrated in [Figure 1](#).

The study consists of 13 study visits: 3 for screening (Weeks -6 [Visit 1], -4 [Visit 2], -2 [Visit 3]), 1 baseline visit (Week 0, [Visit 4]), and 9 treatment visits (Weeks 6 [Visit 5], 13 [Visit 6], 26 [Visit 7], 39 [Visit 8], 52 [Visit 9], 65 [Visit 10], 78 [Visit 11], 91 [Visit 12], and 104 [Visit 13]). Visits 5-13 are to be conducted within  $\pm 7$  days of the scheduled time.

**Figure 1 Study flow chart**

## 2. STUDY OBJECTIVES

### 2.1 Primary objective

Primary Objective:	Outcome Measure:
To assess the efficacy of rosuvastatin 20 mg compared to placebo on slowing progression of carotid intima-media thickness (CIMT) over 104 weeks in Chinese subjects with subclinical atherosclerosis	Annualized rate of change in mean of the maximum (MeanMax) CIMT measurements from each of the 12 carotid artery sites based on all scans performed during the 104-week study period

### 2.2 Secondary objectives

Secondary Objective:	Outcome Measure :
To assess the efficacy of rosuvastatin 20 mg compared to placebo over 104 weeks on slowing progression of intima-media thickness (IMT) in carotid artery segments and on blood lipids in Chinese subjects with subclinical atherosclerosis	
 
• Annualized rate of change in the MeanMax IMT of the near and far walls of the right and left common carotid artery (CCA)
 
• Annualized rate of change in the MeanMax IMT of the near and far walls of the right and left carotid bulb
 
• Annualized rate of change in the MeanMax IMT of the near and far walls of the right and left internal carotid artery (ICA)
 
• Annualized rate of change in the mean of the mean (MeanMean) IMT of the near and far walls of the right and left CCA
 
• Change in LDL-C, total cholesterol, HDL-C, triglycerides, non-HDL-C, apolipoprotein (Apo) B, ApoA-I, non-HDL-C/HDL-C, and ApoB/ApoA-I
 

### 2.3 Safety objectives

Safety Objective:	Outcome Measure :
To assess the safety and tolerability of rosuvastatin 20 mg compared to placebo over 104 weeks in Chinese subjects with subclinical atherosclerosis	Safety assessments will include AEs, serious adverse events (SAEs), AEs leading to discontinuation, changes in clinical laboratory analyses (chemistry, hematology, and urinalysis), vital signs, 12-lead electrocardiograms (ECGs), and physical examination

### **3. SUBJECT SELECTION, ENROLLMENT, RANDOMIZATION, RESTRICTIONS, DISCONTINUATION AND WITHDRAWAL**

Each subject should meet all of the inclusion criteria and none of the exclusion criteria for this study. Under no circumstances can there be exceptions to this rule.

#### **3.1 Inclusion criteria**

For inclusion in the study, subjects should fulfill the following criteria:

1. Provision of informed consent prior to any study-specific procedures
2. Male aged  $\geq 45$  and  $< 70$  years or female aged  $\geq 55$  and  $< 70$  years
3. Subjects with only hypertension (as defined blood pressure  $\geq 140/90$  mmHg or on antihypertensive treatment) and age as CVD risk factors and subjects without hypertension who have 3 or more other risk factors (including age) must have:
  - Fasting LDL C of  $\geq 120$  mg/dL (3.1 mmol/L) and  $< 160$  mg/dL (4.1 mmol/L)Subjects without hypertension who have fewer than 3 other risk factors (including age) must have:
  - Fasting LDL-C of  $\geq 120$  mg/dL (3.1 mmol/L) and  $< 190$  mg/dL (4.9 mmol/L)
4. Triglycerides  $< 500$  mg/dL (5.65 mmol/L) at Visit 1 (Week -6)
5. HDL-C levels  $\leq 60$  mg/dL (1.6 mmol/L) at Visit 1 (Week -6)
6. Maximum IMT  $\geq 1.2$  mm and  $< 3.5$  mm at any location in the carotid ultrasound scans conducted at both Visit 2 (Week -4) and Visit 3 (Week -2)
7. Willing to follow all study procedures including study visits, fasting blood draws, and compliance with study treatment regimen

#### **3.2 Exclusion criteria**

Subjects should not enter the study if any of the following exclusion criteria are fulfilled:

1. Use of pharmacologic lipid-lowering medications (eg, statins, fibrate derivatives, bile acid binding resins, niacin, or its analogues at doses  $> 400$  mg or prescribed Chinese traditional drugs), including cholesterol-absorption inhibitors (CAIs), and CAI/statin combination, within 12 months prior to Visit 1 (Week -6)
2. Current or recent (within 2 weeks of Visit 1, Week -6) use of supplements known to alter lipid metabolism (eg, soluble fibers [including  $> 2$  teaspoons Metamucil® or psyllium-containing supplement per day] or other dietary fiber supplements, marine

- oils, sterol/stanol products, or other supplement determined at the discretion of the investigator)
3. History of hypersensitivity reactions to other HMG-CoA reductase inhibitors
  4. Pregnant women, women who are breast-feeding, and women of childbearing potential who are not using chemical or mechanical contraception or who have a positive serum pregnancy test
  5. Clinical evidence of coronary artery disease (CAD) or any other atherosclerotic disease such as angina, MI, transient ischemic attack, symptomatic CAD, cerebrovascular accident, percutaneous coronary intervention, coronary artery bypass graft, peripheral arterial disease, abdominal aortic aneurysm
  6. History of cancer (other than basal cell carcinoma) in the past 2 years
  7. Uncontrolled hypertension defined as either a mean resting diastolic blood pressure of  $\geq 110$  mmHg or a resting systolic blood pressure of  $\geq 180$  mmHg recorded at any time during the screening period
  8. History of diabetes mellitus or current diabetes mellitus
  9. Uncontrolled hypothyroidism defined as a thyroid stimulating hormone (TSH)  $> 1.5$  times the upper limit of normal (ULN) at Visit 1 or subjects whose thyroid replacement therapy was initiated within the last 3 months
  10. History of heterozygous or homozygous familial hypercholesterolemia or known hyperlipoproteinemia Types I, III, IV, or V (familial dysbetalipoproteinemia)
  11. Use of the disallowed concomitant medications (see Section 7.7.1, except “food supplement taken specifically for lipid lowering”) within 12 months prior to Visit 1 (Week -6)
  12. History of alcohol and/or drug abuse within the past 5 years, that in the investigator’s opinion would jeopardize the patient’s participation in the study or interpretation of the data
  13. Active liver disease or hepatic dysfunction as defined by elevations of  $\geq 1.5$  x ULN at Visit 1 (Week -6) in any of the following liver function tests: alanine aminotransferase (ALT), aspartate aminotransferase (AST), or bilirubin
  14. Serum creatine kinase (CK)  $> 3$  x ULN at Visit 1 (Week -6)
  15. Serum creatinine  $> 2.0$  mg/dL (177 mmol/L) recorded during the screening period
  16. Participation in another investigational drug study, and having ingested investigational drug  $\leq 4$  weeks before enrollment in the screening period

17. Previous randomization in the present study
18. History of a significant medical or psychological condition that, in the opinion of the investigator, would compromise the subject's safety or successful participation in the study
19. Involvement in the planning and/or conduct of the study (applies to both AstraZeneca staff and/or staff at the study site)

For the procedures for withdrawal of incorrectly enrolled subjects, see Section 3.4.

### 3.3 Subject enrollment and randomization

Investigator(s) should keep a record, the subject screening log, of subjects who entered prestudy screening.

The investigator(s) will:

1. Obtain signed informed consent from the potential subject before any study-specific procedures are performed.
2. Assign each potential subject a unique enrollment number, beginning with "E#" via interactive web/voice response system (IWRS/IVRS).
3. Determine subject eligibility; see Sections 3.1 and 3.2.
4. Assign each eligible subject a unique randomization code via IWRS/IVRS.

At the start of the screening period, each subject must be allocated an enrollment code (E-code) **CC/** 

At the end of the screening period, subjects who satisfy the entry criteria will be randomly assigned in a 1:1 ratio to 1 of the following 2 treatment groups: rosuvastatin 20 mg or placebo (see Section 3.5). Randomization codes will be assigned strictly sequentially as subjects become eligible for randomization. If a subject withdraws from participation in the study, then his/her enrollment/randomization code cannot be reused. Once a randomization number has been assigned, no attempt should be made to use that number again.

### 3.4 Procedures for handling incorrectly enrolled or randomized subjects

Incorrectly enrolled or randomized subjects will be discontinued from further study treatment and assessments. Subjects who fail to meet the eligibility criteria should not, under any circumstances, be enrolled or receive investigational product. There can be no exceptions to this rule. Subjects who are enrolled, but subsequently found not to meet all the eligibility

criteria must not be randomized or initiated on treatment, and must be withdrawn from the study.

Where a subject does not meet all the eligibility criteria but is randomized in error, or incorrectly started on treatment, the investigator should inform the AstraZeneca study physician immediately, and a discussion should occur between the AstraZeneca study physician and the investigator regarding whether to continue or discontinue the subject from treatment. The AstraZeneca study physician must ensure all decisions are appropriately documented.

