## **3.10 Criteria for withdrawal**

### **3.10.1 Screen failures**

Screening failures are subjects who do not fulfill the eligibility criteria for the study, and therefore, must not be randomized. These subjects should have the reason for study withdrawal recorded as ‘Incorrect Enrollment’ (ie, subject does not meet the required inclusion/exclusion criteria). This reason for study withdrawal is only valid for screen failures (not randomized subjects).

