## 8.3 Definitions of analysis sets

### 8.3.1 Efficacy analysis sets

Two analysis sets will be used for efficacy evaluation:

- The Intent-to-Treat (ITT) population consists of all randomized subjects. Subjects will be analyzed according to the treatment randomized.
- The per-protocol (PP) population is a subset of the ITT population that includes subjects without any important protocol deviations. The criteria for important protocol deviations will be defined in the statistical analysis plan. Subjects will be analyzed according to the treatment actually received.

The ITT population will be the primary efficacy analysis population. The CIMT analysis will be performed based on both the ITT and PP populations, and lipid and apolipoprotein analyses will be performed on the ITT population only.

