2.1.1 Intent-To-Treat (ITT) analysis set

The primary and secondary efficacy endpoints will be analyzed using the intent-to-treat (ITT) analysis set. The ITT population consists of all randomized subjects. Subjects will be analyzed according to the treatment randomized.

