4.6.3 Post-dosing efficacy observations

During randomized treatment period, efficacy and safety laboratory observations will be listed regardless of whether the subject was taking blinded study drug. Observations will contribute to summaries only if the subject's last dose of blinded drug was as follows:

- CIMT data from ultrasound scans taken more than 31 days after the last dose of study medication will be excluded from the efficacy analysis based on PP population. All CIMT assessments regardless of collection date relative to last dose of study drug will be included in the analysis of primary and secondary endpoints based on ITT population.
- Lipid and lipoprotein measurements will be summarized only if measured on or before the 10th day after the last randomized, double-blind drug dose date.

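### Protocol 3.4 gives two incompatible rules for subjects randomized in error, and its stop on assessments does not match the Early Termination and adverse event procedures

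*Protocol*

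**What the plan says.** Protocol 3.4 deals with ineligible subjects in two paragraphs. The first states without qualification: "Incorrectly enrolled or randomized subjects will be discontinued from further study treatment and assessments". It also bars ineligible subjects from being enrolled or given product, and adds "There can be no exceptions to this rule". The second paragraph concerns a subject who was randomized, or started on treatment, despite failing the criteria. The investigator must tell the sponsor's study physician at once, and the two discuss the case "regarding whether to continue or discontinue the subject from treatment". The decision has to be documented. This paragraph does not mention assessments.

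Other sections bear on the same subjects:

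- Protocol 3.9.1 asks everyone who discontinues product to complete the Early Termination visit. Protocol 4.2.11 and Table 1 add one IMT scan for those leaving after week 26.
- Protocol 6.3.1 collects adverse events until 10 days after the last dose.
- Protocol 4.3 plans no follow-up period.
- On the analysis side, SAP 2.1.1 says "The ITT population consists of all randomized subjects. Subjects will be analyzed according to the treatment randomized", and Protocol 8.3.1 says "The ITT population will be the primary efficacy analysis population".
- For primary and secondary endpoints in ITT, SAP 4.6.3 says "All CIMT assessments regardless of collection date relative to last dose of study drug will be included in the analysis".

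**The concern.** A site that finds it has randomized an ineligible subject cannot tell from Section 3.4 whether treatment must stop or is open to discussion. If it follows the opening sentence literally, it also stops all assessments, including the closing visit and adverse event collection that every other subject stopping product receives.

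The subject remains in the primary analysis population, but the scans that would inform that subject's slope are never taken. At stake are consistent conduct across sites, safety data after the last dose, and completeness of post-randomization CIMT data in ITT.

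**Working it through.** No figure in the plan depends on this rule, and the sample size inputs are redacted. The check is therefore a comparison of texts, a scan count and an illustration of scale.

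**Treatment.** Both paragraphs of Section 3.4 cover subjects already randomized in error. One fixes the outcome (stop) and the other leaves it open (continue or stop). The no-exceptions sentence does not settle this, because it concerns enrolling or dosing ineligible subjects, not what to do once that has happened.

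**Assessments.** The second paragraph is silent here, so the mismatch is with other sections. Protocol 5.2 counts adverse events among the safety assessments, so a literal stop reaches them too.

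| Item | Protocol 3.4, opening sentence | Rule for any subject stopping product |
|---|---|---|
| Early Termination visit | not done | done (3.9.1) |
| Single IMT scan after week 26 | not done | done (4.2.11, Table 1) |
| Adverse events to 10 days after last dose | not collected | collected (6.3.1) |

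**Scans obtained.** SAP 3.1 schedules 7 scans: two before randomization, one each at weeks 26, 52 and 78, and two at the end. The table assumes that earlier scans were all done and that the stop falls between scan visits.

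| Stop occurs | Flat stop | With Early Termination scan | Schedule continued |
|---|---|---|---|
| before week 26 | 2 of 7 | 2 of 7 | 7 of 7 |
| weeks 26 to 52 | 3 of 7 | 4 of 7 | 7 of 7 |
| weeks 52 to 78 | 4 of 7 | 5 of 7 | 7 of 7 |
| weeks 78 to 104 | 5 of 7 | 6 of 7 | 7 of 7 |

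The worst case is 7 − 2 = 5 scans lost. Such a subject has only the two screening scans, nominally 2 weeks apart. The sum of squared deviations of scan time, which governs how well a single slope is estimated, is then (2/52)²/2 = 0.0007 year². With all seven nominal times (−4/52, −2/52, 0.5, 1, 1.5, 2 and 2 years; mean 0.984) it is 11.507 − 7 × 0.984² ≈ 4.74 year². A subject stopped before week 26 therefore says almost nothing about progression.

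**Scale.** The number randomized in error is not in the documents. Let f be the assumed fraction of the 543 randomized subjects who give no slope information, spread equally over the arms. The standard error of the slope difference then grows by 1/√(1 − f), whatever the effect or variance.

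For power, Protocol 1.1 gives the earlier pivotal study's 95% interval (−0.0196 to −0.0093 mm/year; 702 and 282 subjects) and its difference of 0.0145 mm/year. Borrowing these is an assumption, since that study used a different dose and population.

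- SE in that study = (0.0196 − 0.0093)/(2 × 1.96) = 0.00263 mm/year.
- Implied slope SD = 0.00263/√(1/702 + 1/282) = 0.0373 mm/year.
- Here, with n = 543(1 − f)/2 per arm, SE = 0.0373 × √(2/n) and power = Φ(0.0145/SE − 1.96).

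| f (assumed) | Subjects | SE inflation | SE (mm/year) | Power |
|---|---|---|---|---|
| 0 | 0 | none | 0.00320 | 99.5% |
| 1% | 5 | 0.5% | 0.00321 | 99.5% |
| 3% | 16 | 1.5% | 0.00325 | 99.4% |
| 5% | 27 | 2.6% | 0.00328 | 99.3% |
| 10% | 54 | 5.4% | 0.00337 | 99.0% |

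**The case against.** The strongest reply is that the analysis copes. ITT membership depends on randomization alone, the mixed model accepts incomplete profiles (SAP 4.3.2 and 4.3.3), and SAP 3.1 says which readings to use when a randomized subject has no later scan. The treatment discussion involves the sponsor's physician, is documented and takes place under blinding (Protocol 3.6). Recruitment is already complete at 543, so only errors discovered late remain. Keeping these subjects on the full scan schedule could also follow them more closely than eligible subjects who stop early, since no follow-up period is planned.

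Most of this stands, and it limits the point to a small one. It does not remove the contradiction on treatment or the mismatch with the Early Termination procedures. Nor does a model that tolerates missing scans justify instructing sites not to take them. The planned robustness check does not help either: the PP analysis drops subjects with the eligibility failures listed in SAP Appendix A altogether, so it cannot show what their missing scans did.

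A reader might infer more than the documents support:

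- That stopping assessments conflicts with the ITT analysis. It does not: no section removes these subjects from ITT, and the planned model can still be fitted.
- That assessments are removed case by case, inviting bias between sites or arms. The discussion concerns treatment only, and the sentence ending assessments is uniform.
- That a later re-reading of LDL-C or IMT could take subjects out mid-study. Batch reading follows completion or discontinuation (SAP 3.1), eligibility scans are read on receipt (Protocol 12.7.6.1), and the only eligibility re-test of LDL-C mentioned falls between Visits 1 and 2 (SAP Appendix A).
- That cases must be expected because SAP Appendix A lists six eligibility deviations. A list specified in advance is not evidence of occurrence.
- That nothing is gained by stopping data collection because PP already handles ineligibility. Of the 19 exclusion criteria, only the first is in Appendix A.

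**Conclusion.** The point holds as an internal inconsistency with a modest data consequence. Section 3.4 gives two treatment rules that cannot both be followed, and its stop on assessments departs from the procedures for every other subject who stops product. The consequence for ITT is avoidable missing post-randomization CIMT data, at most 5 of 7 scans per affected subject.

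The number of such subjects is unknown and assumed to be few. On that assumption the loss of precision is small: even at an assumed 10% the standard error rises by about 5%. The power figures rest on a slope SD and an effect borrowed from the earlier study. The case therefore rests on consistency, safety data and completeness, not on power.

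**What to change.** First, reconcile the two paragraphs of Protocol 3.4 so that one rule on study treatment applies to subjects randomized in error. This review does not say which.

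Second, and separately, delete the reference to assessments from the opening sentence. State that a randomized subject found ineligible who has not withdrawn consent stays under assessment. That means scheduled CIMT and safety assessments where feasible, and at minimum the Early Termination procedures and adverse event collection that apply to anyone who discontinues product.

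The cost is a short protocol amendment and, for a few subjects, visits already on the schedule. One downside is that these subjects may be followed more fully than other early discontinuers, and the amendment should acknowledge this. The gain is limited to errors discovered while visits are still outstanding; scans already missed cannot be recovered.

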### 3.5 Methods for assigning treatment groups

**CCI**  
[Redacted text block]

### 3.6 Methods for ensuring blinding

Subjects, the investigator, study site personnel, and Sponsor personnel involved with data review and analysis will remain blinded to study treatment throughout the study.

The study treatment will be blinded by providing rosuvastatin and matching placebo tablets, which are indistinguishable from each other in appearance and will be presented in the same packaging.

Medication will be labelled using a unique kit ID number, which is linked to the randomization scheme. IVRS/IWRS will allocate randomization numbers sequentially when sites call the IVRS/IWRS to randomize an eligible subject. IVRS/IWRS will also allocate the kit ID number to be dispensed to the subject.

The treatment codes will be kept strictly within AstraZeneca to safeguard the integrity of the blind of investigator and subjects and hence to minimize any possible bias in data handling.

AstraZeneca patient safety only has access in the cases of emergency whereas AstraZeneca drug supply chain has access to enable investigational product supply. The central laboratory vendor will remain unblinded to the results of all laboratory tests. After screening, subjects and investigational site personnel will be blinded to blood lipid levels. A flag placed by the central laboratory on laboratory reports will alert site personnel that further action is indicated.

### **3.7 Methods for unblinding**

The treatment code should not be broken except in medical emergencies when the appropriate management of the subject requires knowledge of the treatment randomization. Only in the case of a medical emergency, individual treatment codes, indicating the treatment randomization for each randomized subject, will be available to the investigator(s) or pharmacists from the IVRS/IWRS.

Routines for unblinding in the case of an emergency will be described in the IVRS/IWRS user manual that will be provided to each center. The investigator will document and report the action to AstraZeneca, without revealing the treatment given to the subject to the AstraZeneca staff.

AstraZeneca retains the right to break the code for SAEs that are unexpected and are suspected to be causally related to an investigational product and that potentially require expedited reporting to regulatory authorities. Treatment codes will not be broken for the planned analyses of data until all decisions on the evaluability of the data from each individual subject have been made and documented.

